- Presence of signs or symptoms that could confound or confuse assessment of study vaccine reactogenicity. For subjects with injection site or systemic signs or symptoms, or with an acute illness, including an oral temperature greater than or equal to 100°F, the subsequent study vaccination should be postponed/deferred until signs, symptoms, or acute illness have resolved, or are improving as further specified below, and if within the acceptable protocol-specified window for Dose 2 (Group 1 and Group 2, Day 22+7), or Dose 3 (Group 2, Day 43+7). No exceptions to the protocol-specified window will be made. **Note for afebrile, acute illness only:** If a subject is afebrile, his/her acute illness is nearly resolved with only minor residual symptoms remaining, this occurs within the acceptable protocol-specified window for Dose 2 (Group 1 and Group 2, Day 22+7), or Dose 3 (Group 2, Day 43+7) and, in the opinion of the site principal investigator or appropriate sub-investigator, the residual symptoms will not interfere with the ability to assess safety parameters as required by the protocol, the subject may receive the subsequent study vaccination without further approval from the DMID Medical Officer. No exceptions to the protocol-specified window will be made.

- Grade 3 solicited or unsolicited AE that is ongoing, whether or not it is improved or resolving.
- Any unresolved or continuing Grade 2 AE that has not decreased in severity to Grade 1 or less.
- An unresolved or continuing Grade 1 AE is permissible following the documented determination by the site principal investigator or appropriate sub-investigator, that it would not render study vaccination unsafe or interfere with the evaluation of responses.
- Grade 3 solicited or unsolicited AE that occurs without alternative etiology in the 8 days following each study vaccination.

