6.3 Modification of Study Intervention/Investigational Product for a Subject

There will be no dose modifications. If a subject's study vaccination is deferred, it should be rescheduled to occur within the acceptable protocol-specified window for that visit. No exceptions to the protocol-specified window will be made.

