- Concomitant medications (solicitation only for receipt of any non-study influenza vaccines, including those that are experimental, what type (inactivated or live attenuated), what subtype (e.g., A/H3, A/H5, A/H9) and approximate date of vaccination will be recorded on the appropriate DCF, if known and not previously collected) will be recorded on the appropriate DCF. AEs limited to MAAEs, including NOCMCs and PIMMCs, and SAEs that have occurred since the previous clinic visit or contact will be solicited
- A targeted physical examination, including an assessment for signs suggestive of PIMMCs, may be performed, if indicated based on review of interim medical history, by a study clinician licensed to make medical diagnoses and listed on the Form FDA 1572 as the site principal investigator or sub-investigator.
- Approximately 10 mL of venous blood will be collected for serum antibody assays.
- Approximately 10 mL of venous blood will be collected for future research from subjects who consent, either by signing an informed consent form that includes collection of future use samples as a condition of study participation or by indicating that they opt in to sample collection for future use if the informed consent form allows the option to choose that option.

**8.2.10 Visit 11, Day 387, Safety Follow-up, Phone Call
(Window: 365 (± 14) days post Dose 2)**

Subjects will be contacted by phone to query for safety events. AEs limited to MAAEs, including NOCMCs and PIMMCS, and SAEs that have occurred since the previous clinic visit or contact will be solicited. Based on the information, subjects may be asked to return to the clinic for evaluation.

8.3 Follow-up Visits, Group 2

Follow-up visits are scheduled in reference to vaccination dates as indicated for each visit window.

**8.3.1 Visit 02, Day 4, Memory Aid Review, Phone Call
(Window: 3 (± 1) days post Dose 1)**

Study personnel will contact subjects by phone to solicit any AE/SAE and concomitant medication information (including solicitation for receipt of any non-study influenza vaccines, including those that are experimental, what type (inactivated or live attenuated), what subtype (e.g., A/H3, A/H5, A/H9) and approximate date of vaccination will be recorded on the appropriate DCF, if known and not previously collected) and review information on their memory aid. Based on the information, subjects may be asked to return to the clinic for evaluation.

**8.3.2 Visit 03, Day 8, Clinic Visit

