(Window: 7 (± 2) days post Dose 1)**

- Interim medical history, including an assessment for new medical conditions, stability of chronic diseases, and symptoms suggestive of PIMMCs, will be obtained by interview of subjects and any changes since the previous clinic visit or contact will be noted.
- Memory aid information will be reviewed with subjects.
- All concomitant medications (including solicitation for receipt of any non-study influenza vaccines, including those that are experimental, what type (inactivated or live attenuated), what subtype (e.g., A/H3, A/H5, A/H9) and approximate date of vaccination will be recorded on the appropriate DCF, if known and not previously collected) will be recorded on the appropriate DCF.
- All AE/SAEs will be recorded on the appropriate DCF.

- A targeted physical examination, including an assessment for signs suggestive of PIMMCs, may be performed, if indicated based on review of interim medical history, by a study clinician licensed to make medical diagnoses and listed on the Form FDA 1572 as the site principal investigator or sub-investigator.
- The first vaccination site will be examined.
- Approximately 10 mL of venous blood will be collected for safety labs, WBC, Hgb, PLT, ALT, T. Bili, Cr, and performed by the central (clinical) laboratory.
- Approximately 10 mL of venous blood will be collected for future research from subjects who consent, either by signing an informed consent form that includes collection of future use samples as a condition of study participation or by indicating that they opt in to sample collection for future use if the informed consent form allows the option to choose that option.

8.3.3 Visit 04, Day 22, Dose 2, Clinic Visit (Window: 21 (+7) days post first study vaccination)

- Eligibility criteria will be reviewed with subjects prior to the vaccination to ensure continued eligibility.
- For a subject to receive the vaccination, refer to [section 5.2.3](#) for subsequent dose eligibility criteria.
- Interim medical history, including an assessment for new medical conditions stability of chronic diseases and symptoms suggestive of PIMMCs, will be obtained by interview of subjects prior to the vaccination and any changes since the previous clinic visit or contact will be noted.

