- Interim medical history, including an assessment for new medical conditions, stability of chronic diseases, and symptoms suggestive of PIMMCs, will be obtained by interview of subjects and any changes since the previous clinic visit or contact will be noted.
 - Memory aid information will be reviewed with subjects.
 - All concomitant medications (including solicitation for receipt of any non-study influenza vaccines, including those that are experimental, what type (inactivated or live attenuated), what subtype (e.g., A/H3, A/H5, A/H9) and approximate date of vaccination will be recorded on the appropriate DCF, if known and not previously collected) will be recorded on the appropriate DCF.
 - All AE/SAEs will be recorded on the appropriate DCF. Note: for subjects who discontinued from the receipt of Dose 2, AEs will be limited to SAEs and MAAEs, including NOCMCs and PIMMCs.

- A targeted physical examination, including an assessment for signs suggestive of PIMMCs, may be performed, if indicated based on review of interim medical history, by a study clinician licensed to make medical diagnoses and listed on the Form FDA 1572 as the site principal investigator or sub-investigator.
- The second vaccination site will be examined.
- Approximately 10 mL of venous blood will be collected for safety labs WBC, Hgb, PLT, ALT, T. Bili, Cr, and performed by the central (clinical) laboratory.
- Approximately 10 mL of venous blood will be collected for future research from subjects who consent, either by signing an informed consent form that includes collection of future use samples as a condition of study participation or by indicating that they opt in to sample collection for future use if the informed consent form allows the option to choose that option.

8.3.6 Visit 07, Day 43, Dose 3, Clinic Visit (Window: 21 (+7) days post Dose 2)

- Eligibility criteria will be reviewed with subjects prior to the vaccination to ensure continued eligibility.
- For a subject to receive the third vaccination, refer to [section 5.2.3](#) for subsequent dose eligibility criteria.
- Interim medical history, including an assessment for new medical conditions, stability of chronic diseases, and symptoms suggestive of PIMMCs, will be obtained by interview of subjects and any changes since the previous clinic visit or contact will be noted.

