11.6.1 Analysis Populations

The Safety Analysis population includes all subjects who received at least one dose of study vaccine.

The modified intent-to-treat (mITT) population includes all subjects who received at least one dose of study vaccine and contributed both pre- and at least one post-study vaccination venous blood samples for immunogenicity testing (HAI or Neut antibody assays) for which valid results

were reported. For analyses using the mITT population, subjects in Group 2 who discontinue treatment after receiving the single IIV4 dose (Dose 1) but prior to receiving the first dose of the H7N9 vaccine (Dose 2) will be analyzed with group 3. All other subjects will be grouped based on randomized treatment arm.

The per protocol (PP) population includes all subjects in the mITT subset with the following exclusions:

- Data from all available visits for subjects found to be ineligible at baseline.
- Data from all visits subsequent to major protocol deviations, such as:
 - Second or third study vaccination not received,
 - Second or third study vaccination received out of window,
 - Receipt of non-study licensed live vaccine within 30 days before or after each study vaccination,
 - Receipt of non-study licensed inactivated vaccine within 14 days before or after each study vaccination,
 - Receipt of immunosuppressive therapy (e.g., corticosteroids) within 30 days before or after each study vaccination.
- Data from any visit that occurs substantially out of window.

For analyses using the PP population, subjects will be grouped based on study vaccinations received.

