4.4.5. Selection and Timing of Dose for Each Subject

Each subject is to be randomly assigned to a study group which will define the number and timing of AS03 adjuvanted 2017 A/H7N9 vaccinations. The first dose takes place on the day of randomization and will include vaccination with IIV4 for all subjects. Subjects in Group 1 will also receive the first A/H7N9 vaccination at the randomization visit. The second dose, a single A/H7N9 vaccination, if applicable, takes place approximately 21 days after the first dose (protocol defined window of 21-28 days post first dose). The third dose, a single A/H7N9 vaccination, if applicable, takes place approximately 21 days after the second dose (protocol defined window of 21-28 days post second dose).

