6.3.3. Per Protocol Population

The per protocol (PP) population includes all subjects in the mITT subset with the following exclusions:

- Data from all available visits for subjects found to be ineligible at baseline.
- Data from all visits subsequent to major protocol deviations, such as:
 - Second or third dose not received,
 - Second or third dose received out of window,
 - Receipt of non-study licensed live vaccine within 30 days before or after each study vaccination,
 - Receipt of non-study licensed inactivated vaccine within 14 days before or after each study vaccination,
 - Receipt of immunosuppressive therapy (e.g., corticosteroids) within 30 days before or after each study vaccination.
- Data from any visit that occurs out of window by more than one day.

For analyses using the PP population, subjects will be grouped based on study vaccinations received - subjects in Group 2 who discontinue treatment after receiving the single IIV4 dose (Dose 1) but prior to receiving the first dose of the H7N9 vaccine (Dose 2) will be analyzed with Group 3.

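### Protocol 5.2.3 and 8.3.6 give Group 2's Dose 3 different windows when Dose 2 is late but in window, so one section can bar a deferred dose that the other permits

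*Protocol*

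**What the plan says.** Protocol 5.2.3 lists the conditions under which a second or third dose is withheld or deferred. It gives the Group 2 Dose 3 window as Day 43+7 in three places: the general deferral rule, the note on afebrile acute illness, and the rule on Grade 3 laboratory values. The general and laboratory rules share the wording "or Dose 3 (Group 2, Day 43+7). No exceptions to the protocol-specified window will be made", and the afebrile note also closes by ruling out exceptions.

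Protocol 8.3.6 (Group 2, Visit 07, Dose 3) counts the same dose from the previous one: "Window: 21 (+7) days post Dose 2". SAP 4.4.5 agrees with it: "protocol defined window of 21-28 days post second dose". In Protocol Table 2b and Appendix A (and SAP Table 4) the +7 for this visit sits on the row counted from Dose 2. The D43 on the row counted from Dose 1 carries no window.

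Dose 2 has its own tolerance in Protocol 8.3.3: "Window: 21 (+7) days post first study vaccination".

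Protocol 6.3 says of a deferred vaccination that "it should be rescheduled to occur within the acceptable protocol-specified window for that visit. No exceptions to the protocol-specified window will be made".

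Both per-protocol definitions remove data after a mistimed dose: "Second or third study vaccination received out of window" in Protocol 11.6.1 and "Second or third dose received out of window" in SAP 6.3.3. SAP Table 18 has lines for Study Dose 3 out of window.

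**The concern.** Each rule is worded as absolute: 5.2.3 directly, and the 8.3.6 visit window through 6.3. They are anchored differently, and a perfectly conforming late Dose 2 is enough to separate them. A site deciding on a deferred Dose 3 has to read both, because 8.3.6 sends it to 5.2.3 for eligibility.

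Dose 3 is Group 2's second H7N9 dose, so that arm's primary H7N9 endpoint at Day 64 depends on it. A dose wrongly withheld cannot be recovered: vaccinated subjects are not replaced (Protocol 5.2.4) and missing values are not imputed (Protocol 11.6.4, SAP 6.5). Group 1's second H7N9 dose is not exposed. It is counted from Day 1, so Day 22+7 in 5.2.3 and 21 (+7) days after Dose 1 in 8.2.3 are the same days.

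**Working it through.** **Inputs**
- Dose 1 is on Day 1.
- Dose 2, Group 2: 21 to 28 days after Dose 1, i.e. Day 22+d with d = 0 to 7 (Protocol 8.3.3).
- Dose 3, read literally from Protocol 5.2.3: Days 43 to 50.
- Dose 3, from Protocol 8.3.6 and SAP 4.4.5: 21 to 28 days after Dose 2.

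**Formulas**
- Window counted from Dose 2: (22+d)+21 to (22+d)+28 = Day 43+d to Day 50+d.
- Days satisfying both rules: Day 43+d to Day 50, which is 50-(43+d)+1 = 8-d days.
- Days allowed by 8.3.6 and the SAP only: Day 51 to Day 50+d, which is d days.
- Days inside the literal 5.2.3 range only: Day 43 to Day 42+d, which is d days, at intervals of 43-(22+d) = 21-d up to 20 days after Dose 2.

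**Reproducing the plan's figure.** At d = 0 the window counted from Dose 2 is Days 43 to 50, so Day 43+7 is recovered exactly, but only for Dose 2 on Day 22.

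| Dose 2 day | d | Window from Dose 2 | Days meeting both | Permitted by 8.3.6 and SAP, barred by 5.2.3 |
|---|---|---|---|---|
| 22 | 0 | 43-50 | 8 | none |
| 23 | 1 | 44-51 | 7 | 51 |
| 24 | 2 | 45-52 | 6 | 51-52 |
| 25 | 3 | 46-53 | 5 | 51-53 |
| 26 | 4 | 47-54 | 4 | 51-54 |
| 27 | 5 | 48-55 | 3 | 51-55 |
| 28 | 6 | 49-56 | 2 | 51-56 |
| 29 | 7 | 50-57 | 1 | 51-57 |

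**How much deferral is needed.** The 21-day target is Day 43+d. For every d from 0 to 7 it lies within Days 43 to 50, so a Dose 3 given on target satisfies both rules. To pass Day 50, Dose 3 must slip at least 51-(43+d) = 8-d days beyond target: 7 days when Dose 2 was one day late, and 1 day when it was seven days late.

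**The case against.** The best defence is that Day 43+7 is shorthand for the Day 43 visit with its own tolerance. Day 43 is part of that visit's title in 8.3.6. Section 6.3 ties the window to the visit, and 8.3 says "Follow-up visits are scheduled in reference to vaccination dates as indicated for each visit" window. Every schedule table puts the +7 on the Dose 2 row. This may well be what was meant, but 5.2.3 does not say so. The same phrase gives Dose 2 as Day 22+7, which is counted from Dose 1, so the parallel reading of Day 43+7 is study Days 43 to 50. It cannot be counted from Dose 2 either, because D43 on that row is the study Day 64 visit.

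Several stronger readings are tempting, and the documents do not support them.

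- *A late Dose 2 leaves no usable day for Dose 3.* The windows always overlap, and the overlap always includes the target day.
- *5.2.3 authorises a 14-day interval.* Days 43 to 42+d do fall inside its literal range, and at d = 7 Day 43 is 43-29 = 14 days after Dose 2. But 5.2.3 is a rule for withholding and deferring. It does not itself authorise bringing a dose forward from the 8.3.6 schedule.
- *The per-protocol rule has two answers.* The SAP states one dose window, in 4.4.5. What remains open is how sites classify deviations under the protocol, which feed the per-protocol review in SAP 7.2.
- *The comparison of schedules is biased.* Only Group 2 is exposed, but neither direction nor size can be derived. The primary immunogenicity population is mITT (SAP 8.1), although the regression on treatment schedule uses per-protocol data (SAP 8.3.2).
- *All 60 Group 2 subjects are at risk.* Sixty is the size of the arm and therefore a ceiling.

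**Conclusion.** The inconsistency is real and narrow. For any in-window Dose 2 on Days 23 to 29, the two statements of the Dose 3 window differ by d days at each end. The end that matters in practice is the late one. On Days 51 to 50+d, 8.3.6 and the SAP permit a deferred Dose 3 that 5.2.3, read literally, bars without exception. The same subject may therefore be dosed or refused, and the same dose may be recorded as conforming or as a deviation, according to the section the site uses.

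This rests on reading Day 43+7 as study days counted from Day 1, and on Dose 2 using its full permitted tolerance. Both a late Dose 2 and a Dose 3 on a disputed day are needed. The documents give no expected frequency for either, so the number affected and any bias are unknown. No sample-size or power figure changes. The correction is still worth making before it is needed, because a dose withheld on this ground cannot be restored.

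**What to change.** Reconcile the three mentions in Protocol 5.2.3 with Protocol 6.3, 8.3.6, Appendix A and SAP 4.4.5, so that Group 2's Dose 3 has one window with one stated anchor. Use that window for deviation classification, the per-protocol exclusion and the Dose 3 out-of-window lines in SAP Table 18. Which window is right is for the sponsor to decide.

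If dosing has already taken place, list any Group 2 subjects whose Dose 3 was given or withheld on a day that the two passages treat differently.

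The cost is a clarification memo or short protocol amendment and, if the SAP wording changes, one line there. No extra subjects, visits or samples are needed.

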5.2.4 Handling of Withdrawals and Discontinuation of Treatment

The primary reason for withdrawal from this trial will be recorded on the Study Status data collection form (DCF). Subjects will be encouraged to complete the Early Termination Visit. The Early Termination Visit procedures are listed in [Section 8.5](#).

Although subjects are free to withdraw at any time or may be withdrawn by the site principal investigator or appropriate sub-investigator at any time (see [Section 5.2.3](#)), those subjects do not receive Dose 2 or Dose 3 of study vaccine will be encouraged to remain in this trial for follow-up safety assessments (may be conducted by phone call rather than in person) continuing through approximately 12 months after their last study vaccination. These subjects will also be encouraged to provide a venous blood sample for immunogenicity assays at approximately 21 days and 180 days after their last study vaccination, if applicable. See the protocol-specific Manual of Procedures (MOP) for alternate follow-up requirements.

Every attempt will be made to follow all AEs, including solicited injection site and systemic reactions, unsolicited non-serious AEs, SAEs and MAAEs, including NOCMCs and PIMMCs, ongoing at the time of early withdrawal through resolution as per applicable collection times defined for the specific type of AE.

In the case of subjects who fail to appear for a follow-up safety assessment, extensive effort (i.e., three documented contact attempts via phone calls made on separate occasions and followed by a certified letter) will be made to locate or recall them, or at least to determine their health status. These efforts will be documented in the subject's study records.

Subjects who withdraw, or are withdrawn or terminated from this trial, or are lost to follow-up after signing the informed consent form (ICF), randomization, and receipt of study vaccine will not be replaced. However, if a subject withdraws after signing the ICF, but before randomization and/or receipt of study vaccine, they may be replaced.

5.2.5 Termination of Study

Although the sponsor has every intention of completing this trial, it reserves the right to terminate this trial at any time for clinical or administrative reasons. Reasons for termination include, but are not limited to, study closure due to DSMB review and recommendation and at the discretion of DMID.

6 STUDY INTERVENTION/INVESTIGATIONAL PRODUCT

6.1 Study Product Description

2017 H7N9 IIV

Sanofi Pasteur has developed a monovalent 2017 H7N9 IIV manufactured from a reverse genetics-derived reassortant virus containing the HA and NA from influenza A/Hong Kong/125/2017 (H7N9) and the PB2, PB1, PA, NP, M and NS from A/Puerto Rico/8/1934 (H1N1). The manufacturing process for the production of this monovalent 2017 A/H7N9 IIV is similar to the manufacturing process used to produce the licensed IIV Fluzone® family of products.

The HA content of the A/H7N9 vaccine formulation has been determined by [REDACTED]

this clinical trial, the labeling of the original [REDACTED]

[REDACTED] The vaccine preparation has been adjusted to [REDACTED]

[REDACTED] The final vaccine preparation is [REDACTED]

PBS diluent

The PBS diluent was produced in accordance with the commercial process utilized in manufacture of [REDACTED] buffer/diluent for the formulation of Fluzone®, influenza virus vaccine.

AS03 Adjuvant [Adjuvant System AS(03)]

AS03 is GSK's proprietary [REDACTED]

Fluzone® Quadrivalent Influenza Vaccine (IIV4)

IIV4 manufactured by Sanofi Pasteur for IM injection is an inactivated influenza vaccine, prepared from influenza viruses propagated in embryonated chicken eggs. Fluzone® Quadrivalent is formulated to contain HA of each of the following four influenza strains recommended for the 2017-2018 influenza season: A/Michigan/45/2015 X-275 (H1N1), A/Hong Kong/4801/2014 X-263B (H3N2), B/Phuket/3073/2013 (B Yamagata lineage), and B/Brisbane/60/2008 (B Victoria lineage). The single-dose, pre-filled syringe (0.5 mL)

without thimerosal, clear plunger rod, without needle will be supplied as package of 10 syringes.

